6.12.1.3 Measurement of Blood Plasma Concentration (DU-176b Group Only)

The drug concentration measurement laboratory (Q² Solutions) will measure the plasma DU-176 concentration promptly after receiving the specimens. The plasma drug concentration will be measured by liquid chromatography tandem mass spectrometry (LC-MS/MS).

6.12.2 Measurement of Pharmacodynamic Indicators and Biomarkers

6.12.2.1 Times of Blood Sampling for Measuring Pharmacodynamic Indicators

At the eligibility assessment examination (Visit 1) and Week 8 of the study treatment period (Visit 3), blood samples for measuring PD indicators (PT and aPTT) will be collected, and the date of sampling and the time of sampling will be entered on the case report form. The timing of the blood sampling in Week 8 of the study treatment period (Visit 3) will be the same as the timing of the blood sampling for measuring plasma drug concentration (see "6.12.1.1 Blood Sampling Times and Meal Records for Measuring Plasma Drug Concentration").

6.12.2.2 Times of Blood Sampling for Measuring Biomarkers

At the eligibility assessment examination (Visit 1) and Week 8 of the study treatment period (Visit 3), blood samples for measuring biomarkers (D-dimer and F1+2) will be collected, and the date of sampling and the time of sampling will be entered on the case report form. The timing of the blood sampling in Week 8 of the study treatment period (Visit 3) will be before the study drug is taken (the trough time).

6.12.2.3 Method of Blood Sampling for Measuring Pharmacodynamic indicators Biomarkers, Plasma Isolation, and Storage

A quantity of 4.5 mL of venous blood will be collected using a single 4.5 mL vacuum blood sampling tube containing citric acid. Promptly after sampling, the plasma will be separated and fractionated into a container for submission, and stored frozen at the study site until it is collected by SRL, Inc.

6.12.2.4 Measurement of Pharmacodynamic Indicators and Biomarkers

Centralized measurement of PD indicators and biomarkers will be performed at SRL, Inc. SRL, Inc. will measure PD indicators (PT and aPTT) and biomarkers (D-dimer and F1+2) promptly after receiving specimens. The results of measurement will not be disclosed to the study site or the Sponsor, except in cases where this is unavoidable, such as when action is taken to treat adverse events or in emergencies.

6.13 Adverse Events

If an adverse event occurs between the initiation of study treatment and the examination at completion of study treatment or the examination at discontinuation, †††† a survey will be performed according to "9.4 Adverse Event Information to Be Reported" and the information will be entered on the case report form.

During study drug interruption and after study drug discontinuation, a survey to find whether any serious adverse events have occurred will be performed at least every 8 weeks, and if they have, a survey will be performed according to "9.4 Adverse Event Information to Be Reported" and the information will be entered on the case report form. Occurrence of any serious adverse events will be monitored until the final follow-up examination and will be reported in accordance with the Section "9.6.2 Action When a Serious Adverse Event Occurs."

6.14 Efficacy Events

If the following efficacy events occur between randomization and the examination at completion of study treatment or the examination at discontinuation, †††† a survey will be performed according to "9.4 Adverse Event Information to Be Reported" and a survey of information such as the event classification, details of the event classification, and, depending on the situation in which the event occurred, cerebrovascular events (including intracranial bleeding), SEEs, cardiac ischemic events, and bleeding events, will be performed, and the information will be entered on the case report form. Copies of findings such as head imaging scans and ECGs that form the evidence for the diagnosis of the efficacy event will be submitted to the Sponsor. If the efficacy event that occurred is a stroke, it will be assessed using the modified Rankin Scale at (approximately) 1 month following stroke onset, and the assessment will be entered on the case report form.

Stroke

††††: For subjects withdrawn from study participation

- SEE
- MI
- TIA
- Hospitalization due to cardiovascular disease (CV) condition (including hospitalizations for bleeding)
- All-cause mortality (death due to CV and mortality due to all other causes)
- Venous thromboembolic event (VTE) (pulmonary thromboembolism [PTE] and deep vein thrombosis [DVT])

During study drug interruption and after study drug discontinuation, a survey of the above will be performed at least every 8 weeks, and the information will be entered on the case report form.

If the subject who developed the efficacy event is hospitalized at, or making visits to, another medical institution, the investigator or subinvestigator will contact the subject's physician at the medical institution where the subject is hospitalized or making visits, and make every attempt to obtain detailed information, as far as possible.

6.15 Bleeding Events

If a bleeding event (see 9.1 Bleeding Events) occurs between the initiation of study treatment and the examination at completion of study treatment or the examination at discontinuation, to survey will be performed according to "9.4 Adverse Event Information to Be Reported" and a survey of information such as the event classification, details of the event classification, and depending on the situation in which the event occurred, laboratory tests, whether blood transfusion was performed, and the amount of blood transfused, will be performed, and the information will be entered on the case report form. In response to requests from the Clinical Bleeding Event Committee or the Sponsor, the investigator or subinvestigator will provide information such as imaging scan results that form the evidence for the diagnosis.

During study drug interruption and after study drug discontinuation, a survey of the above will be performed at least every 8 weeks, and the information will be entered on the case report form.

If the subject who developed the bleeding event is hospitalized at, or making visits to, another medical institution, the investigator or subinvestigator will contact the subject's physician at the medical institution where the subject is hospitalized or making visits, and

^{††‡‡} For subjects withdrawn from study participation

make every attempt to obtain detailed information, as far as possible.

6.16 Long-term Storage of Clinical Specimens for Genomic and Genetic Analysis

Long-term storage (banking) of DNA specimens extracted from the subjects' blood by the following procedure will be performed, in preparation for the future case where new genomic or genetic information relating to the response to DU-176b (pharmacokinetic [PK] or PD) is obtained, or a serious adverse drug reaction is observed in a clinical study and genomic and genetic analysis is performed to discover the cause. A new research plan will be specified when the specific details of genomic and genetic analysis have been finalized.

Details of the handling of specimens are shown separately in the Procedures for the Handling and Transportation of Banking Specimens.

6.16.1 Targeted Specimens

At study sites where banking is approved, an explanation of banking will be given, and specimens will be sampled from subjects who provide informed consent (in-person consent only). The investigator or subinvestigator will enter the dates of informed consent on the case report forms of subjects who provide informed consent for banking. The investigator or subinvestigator will enter any information such as medical history (for example, allogeneic bone marrow transplantation) that may affect genomic or genetic information on the case report forms.

6.16.2 Sampling of Banking Specimens (Blood Sampling)

At any visit during the study treatment period from Visit 2 onwards, 7 mL of venous blood will be sampled from a cutaneous vein in the forearm of each subject. The sampled blood will be stored frozen as whole blood until the specimens are collected (at a temperature setting of -20° C or lower). The investigator or subinvestigator will enter the date of blood sampling on the case report form. So that the subjects' personal information is not leaked to external parties, the specimens will be managed by labeling them with codes that are unrelated to the subjects.

6.16.3 Duration of Storage

The duration of storage of banking specimens will be a maximum of 20 years from the day when notification of this study protocol is submitted.

6.16.4 Disclosure of the Results of Genomic and Genetic Analysis Using Banking Specimens

At present, the time when pharmacogenomics investigation using banking specimens will be performed, the method of genomic and genetic analysis, and whether or not the disclosure will be required, have not been determined. Accordingly, we do not plan to disclose the results of genomic and genetic analysis to parties such as the investigators or to subjects.

6.16.5 Disposal of Banking Specimens

After the end of the duration of storage, or if the subject withdraws consent during the storage period, banking specimens will promptly be disposed of. However, if genetic analysis has been performed before the end of the duration of storage or before the subject withdraws consent, the data related to these will not be discarded.

7. EFFICACY ENDPOINTS

The following efficacy events observed from randomization up to the examination at completion of study treatment or the examination at discontinuation will be assessed. Efficacy events will be reassessed by a Clinical Efficacy Event Committee independent of the assessment of the investigator or subinvestigator, and the assessment of the Clinical Efficacy Event Committee will be taken as the final assessment.

7.1 Primary Endpoint

For the composite endpoint of stroke and SEE observed from randomization up to the examination at completion of study treatment or the examination at discontinuation, \$\$\\$\\$\$ the time to onset of the initial event will be assessed.

A stroke is defined as an abrupt onset, over minutes to hours, of focal neurological deficit symptoms that are generally in the distribution of a single brain artery (including the retinal artery) and that is not due to an identifiable non-vascular cause (i.e., brain tumor or trauma). The deficit symptoms must either last more than 24 hours or result in death within 24 hours of symptom onset.

A SEE is defined as an abrupt episode of arterial insufficiency associated with clinical or radiologic evidence of arterial occlusion in the absence of other likely mechanisms (e.g., atherosclerosis, instrumentation).

Detailed definitions of stroke and SEE are shown separately in the Procedures for the

Confidential

^{§§§§:} For subjects withdrawn from study participation

Clinical Efficacy Event Committee.

< Rationale and Suitability of Endpoint>

As this is a clinical study to confirm the effect of anticoagulants in preventing cerebroembolic stroke in patients with NVAF, we selected the standard endpoint used for efficacy assessment.

7.2 Secondary Endpoints

For the following endpoints, the time to onset of the initial event observed from randomization up to the examination at completion of study treatment or the examination at discontinuation**** will be assessed. Detailed definitions of individual events are shown separately in the Procedures for the Clinical Efficacy Event Committee and the Procedures for the Clinical Bleeding Event Committee.

- 1) Composite of stroke, SEE, and death due to CV
- 2) Major adverse cardiovascular events (MACE): non-fatal MI, non-fatal stroke, non-fatal SEE, or deaths due to CV or bleeding
- 3) Stroke, SEE, and all-cause mortality
- 4) Net clinical benefit: stroke, SEE, major bleeding, and all-cause mortality
- 5) All-cause mortality

7.3 Other Endpoints

The following endpoints will be used.

- 1) Hospitalization due to CV condition (including hospitalizations for bleeding)
- 2) Modified Rankin Scale (approximately) 1 month after the onset of stroke
- 3) Stroke, SEE, and TIA
- 4) Number of occurrences of stroke and SEE
- 5) VTE (PTE and DVT)

8. PHARMACOKINETIC ENDPOINTS

The plasma DU-176 concentration at Week 8 (Visit 3) during the study treatment period will be assessed.

9. SAFETY ENDPOINTS

The following items observed between the initiation of study treatment and the

^{*****:} For subjects withdrawn from study participation

examination at completion of study treatment or the examination at discontinuation ††††† will be assessed.

- 1) Major bleeding
- 2) Major bleeding and clinically relevant non-major bleeding
- 3) Clinically relevant non-major bleeding
- 4) Minor bleeding
- 5) All bleeding events (composite of major bleeding, clinically relevant non-major bleeding, and minor bleeding)
- 6) Adverse events
- 7) Adverse drug reactions

9.1 Bleeding Events

Bleeding-related adverse events observed between the initiation of study treatment and the examination at completion of study treatment or the examination at discontinuation the discontinuation will be assessed as bleeding events. Bleeding events will be reassessed by a Clinical Bleeding Event Committee independent of the assessment of the investigator or subinvestigator, and the assessment of the Clinical Bleeding Event Committee will be taken as the final assessment.

Bleeding events will be classified into major bleeding, clinically relevant non-major bleeding, and minor bleeding according to the following definitions. Detailed definitions of bleeding events are shown separately in "Procedures for the Clinical Bleeding Event Committee."

9.1.1 Major Bleeding

Overt bleeding that meets at least 1 of the following criteria will be taken to be major bleeding.

- Fatal bleeding
- Retroperitoneal, intracranial, intraocular, intrathecal, intraarticular, or periarticular bleeding, or symptomatic intramuscular bleeding accompanied by compartment syndrome
- Clinically overt bleeding that decreases hemoglobin by at least 2.0 g/dL and requires blood transfusion*
 - *: Transfusion of 1 unit of red cell concentrates or whole blood (about 200 mL) will be converted to a decrease in hemoglobin of 1.0 g/dL. For bleeding related to a surgical

^{†††††:} For subjects withdrawn from study participation

procedure, bleeding in excess of the usual quantity of bleeding for the surgery or procedure will be considered. If there are no data for hemoglobin, the criterion will be bleeding that decreases the hematocrit level by at least 6.0% and requires blood transfusion.

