DU-176b 15 mg or placebo will be administered orally once daily. Administration of the study drug will be continued until the examination at completion of study treatment performed within 60 days after the declaration of completion of the study. Completion of the study will be declared when the planned number of subjects with primary efficacy endpoint events has been collected. The planned mean duration of study treatment is 2 to 2.5 years.

When the investigator or subinvestigator requires to know the study treatment assignment for each subject to determine the subsequent treatment after the final administration of the study drug, the study treatment can be continued until the final follow-up examination after obtaining consent from the subject. The planned duration of the additional study treatment from the examination at completion of study treatment to the final follow-up examination is 3 to 4 months.

Prohibited

Anticoagulants

Concomitant

Thrombolytic drugs

Medication:

Antiplatelet drugs (including over-the-counter drugs containing aspirin) administered to reduce the risk of cardioembolic stroke based on AF, dual antiplatelet therapy

Study Procedures:

See the study procedure and specimen collection schedule (page 5)

Endpoints:

Primary Endpoints

Efficacy: Composite of stroke and SEE

Safety: Major bleeding Secondary Endpoints

Efficacy:

Composite of stroke, SEE, and death due to CV

- Major adverse cardiovascular events (MACE)[†]
- Stroke, systemic embolism, and all-cause mortality
- Stroke, systemic embolism, major bleeding, and all-cause mortality
- All-cause mortality

Safety:

- Major bleeding and clinically relevant non-major bleeding
- Clinically relevant non-major bleeding
- Minor bleeding
- All bleeding events

Primary Statistical Analysis:

For the composite endpoint of stroke and systemic embolism observed from randomization up to the examination at completion of study treatment, the time to onset of the initial event, the treatment group will be compared based on a Cox proportional hazard model with the CHADS₂ score (≤ 2 or ≥ 3) as covariate. (significance level: 5%, 2-sided)

^{†:} Non-fatal myocardial infarction, non-fatal stroke, non-fatal systemic embolism, or deaths due to cardiovascular disease or bleeding

Table of Study Procedure and Specimen Collection Schedule

14010	or state	, 11000	Tage time		· ·	
				Duration of study treatment		
	Flicil	hility	Every 4	Every 8		

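### Does requiring both a hemoglobin fall and a need for transfusion make the major bleeding definition defective?

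*Combined protocol and SAP*

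**What the plan says.** Section 9.1.1 makes an overt bleed major if it meets any one of three criteria: it is fatal; it lies at a listed site (for example intracranial, intraocular or retroperitoneal); or it meets the laboratory criterion, "Clinically overt bleeding that decreases hemoglobin by at least 2.0 g/dL and requires blood transfusion".

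A note to the third criterion says that each transfused unit "will be converted to a decrease in hemoglobin of 1.0 g/dL". Where hemoglobin is not available, the substitute is "bleeding that decreases the hematocrit level by at least 6.0% and requires blood transfusion".

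Section 9.1.2 takes the next tier, overt bleeding that needs treatment and is visually confirmed. Section 9.1.3 puts all remaining overt bleeds under minor bleeding. Section 9.1 refers the finer detail to the bleeding committee's own procedures ("Detailed definitions of bleeding events are shown separately in") and says that the committee's classification "will be taken as the final assessment".

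Major bleeding is the primary safety endpoint in the synopsis. It is also the only bleeding component of a secondary endpoint in section 7.2: "Net clinical benefit: stroke, SEE, major bleeding, and all-cause mortality".

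**The concern.** The word joining the two halves of the laboratory criterion carries a lot of weight. A non-fatal gastrointestinal bleed is not at a listed site, so it can be major only through this criterion. If the treating team judges that no transfusion is needed, the bleed falls to clinically relevant non-major at best, whatever the size of the fall. It then drops out of the primary safety endpoint and does not count as a bleed in net clinical benefit.

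Randomization and blinding protect the comparison with placebo, but they do not protect an absolute rate. The Introduction says that clinical acceptability is to be judged partly against major bleeding rates on available anticoagulants. If those rates came from a wider definition, the trial's rate would look low by comparison. The text also does not say whether the word for requiring transfusion means that blood was given or that it was judged necessary.

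**Working it through.** **1. Is the literal reading right?** Write the rule as: major = fatal, or listed site, or [(hemoglobin fall + 1.0 × units transfused ≥ 2.0 g/dL) and transfusion required]. With no hemoglobin data, a hematocrit fall of at least 6.0% replaces the term in round brackets. For a non-fatal bleed outside the listed sites:

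| Hemoglobin fall (g/dL) | Units | Transfusion required | Major? |
|---|---|---|---|
| 2.0, 3.0 or 5.0 | 0 | no | no |
| 1.0 | 1 | yes | yes |
| 0 | 2 | yes | yes |
| 0.5 | 1 | yes | no |
| no data; hematocrit fall 8% | 0 | no | no |

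The reading is correct.

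**2. Is it a slip?** The joint condition appears in the hemoglobin criterion and again in the hematocrit substitute. The unit conversion fits with it: it sets how the fall is measured and leaves the transfusion condition in place. No other section gives a route to major bleeding through the fall alone or through transfusion alone. The text shows no sign that the condition was unintended.

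**3. Where do the left-out bleeds go?** They are overt by definition, so each one is in all bleeding events (section 9, item 5). Section 9.1.2 counts hospitalization, laboratory tests, imaging, endoscopy and physician-directed interruption of study drug as treatment. A bleed with a large fall would plausibly meet that and, once visually confirmed, enters major plus clinically relevant non-major bleeding. Section 11.4.5.1 analyses both categories by the method used for the primary endpoint.

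**4. How large could the effect on the absolute rate be?** The plan states no figure to reproduce, and the documents do not give the share of bleeds left out. The following is a sensitivity calculation under stated assumptions.

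- Exposure: 400 subjects (section 11.6) × 2 to 2.5 years mean treatment (section 5.2.1) = 800 to 1000 patient-years on active drug, an upper bound with no losses.
- Rate: 1.99%/year (Introduction; edoxaban 15 mg, age 80 or older, another trial, definition not stated), treated here as a rate measured with the clause.
- Expected major bleeds: 800 × 0.0199 = 15.9 and 1000 × 0.0199 = 19.9.
- Exact Poisson 95% limits: 16/800 gives 1.14 to 3.25%/year; 20/1000 gives 1.22 to 3.09%/year.

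If the clause leaves out a share *s* of the bleeds that would otherwise be major, the rate without it is 1.99/(1 − *s*). This gives 2.21, 2.65 and 3.98%/year for *s* = 10, 25 and 50%. These shares are arbitrary.

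The outside rates below are those the Introduction cites for age 80 or older. The share needed for the point estimate is *s* = 1 − 1.99/rate, and the added bleeds are (rate − 1.99)/100 × patient-years, rounded up.

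| Outside rate | Share needed | Added bleeds, point estimate | Added bleeds, upper 95% limit |
|---|---|---|---|
| 4.28%/year (dose-adjusted edoxaban 30 mg) | 54% | 19 to 23 | 7 to 10 |
| 6.77%/year (warfarin) | 71% | 39 to 48 | 24 to 32 |

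The upper limit first reaches 4.28 at 23/800 (4.31) and 30/1000 (4.283). It first reaches 6.77 at 40/800 (6.81) and 52/1000 (6.82).

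**5. Is the assumption behind step 4 sound?** Only in part. All three cited rates come from the same earlier trial. If that trial used the clause, 4.28 and 6.77 include it too, and a clause-free rate should not be set against them. If it did not, 1.99 is already clause-free and should not be inflated. Either way the table tends to overstate the problem.

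**The case for a change.** The strongest argument is that the clause governs a type of bleed for which this population is selected. A history of gastrointestinal bleeding is a qualifying risk in inclusion criterion 4, yet a new non-fatal one counts as major only with a need for transfusion. The endpoint is primary for safety, the Introduction brings in outside rates without giving their definition, and a prespecified sensitivity analysis would cost little. The upper confidence limit would also meet 4.28%/year after only 7 to 10 more bleeds.

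Some of this stands. The documents do not show that a comparison with outside rates would be like for like, and a report that makes one should state both definitions. The protocol text alone also leaves the meaning of requiring transfusion open.

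Neither point makes the definition wrong. The outside comparison rests on one sentence in the Introduction, which names the placebo comparison first. It sets no threshold, and sections 11.4.5 and 11.4.5.1 contain no analysis that carries it out. The 4.28 mark is therefore illustrative and is not a decision rule. The detailed definitions are in the committee procedures, which are outside the supplied documents and may already settle the wording. Section 6.15 provides for recording, as the situation warrants, whether blood was given and how much. A sensitivity analysis without the clause would be an optional extra. It could also be incomplete: scheduled hematology is every 8 weeks (section 6.8), event-related tests are collected as the situation warrants (section 6.15), and missing values are not imputed (section 11.3.3).

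**Conclusion.** The concern does not hold. The literal reading is accurate, but it describes an internally consistent endpoint that is stated twice, contradicted nowhere in the documents and applied under blinding to both arms. It shows no bias between arms. Preferring a criterion based on the fall alone is a preference between definitions.

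The number of affected bleeds cannot be estimated from the documents. With 800 to 1000 patient-years and 1.99%/year taken as a rate under the clause, about 54% of otherwise major bleeds would have to be left out before the point estimate without the clause reached 4.28%/year, and about 71% before it reached 6.77%/year. Nothing in the documents supports shares of that size. The bleeds at issue remain visible in the broader bleeding categories, which are analysed by the same method. The conclusion rests on the protocol text alone; the committee procedures were not available.
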